1) Pediatric International Knee Documentation Committee Subjective Knee Evaluation form (Pedi-IKDC)

- 2) Knee Injury and Osteoarthritis Outcome Score (KOOS)
- 3) Tegner Activity Scale

4) Anterior Cruciate Ligament Return to Sport Index (ACL-RSI) scale.

These 4 outcome measures will be collected at Pre-op, 3months, 6months, return to play, and 2 years. The Pedi-IKDC form is a validated knee-specific questionnaire³⁶ that measures pain, symptoms, and functioning in daily and sport activities.^{37,38} The KOOS form is a validated questionnaire that measures patient-reported pain, symptoms, activities of daily living, sport and recreation and quality of life.^{39,40} The Tegner Activity Scale is a 2-item outcome measure on which participants are asked to describe the peak physical activity intensity prior to ACL injury and at the time of study enrollment. The ACL-RSI is a validated scale that is used to evaluate psychological readiness to return to sport,^{41,42} and includes items that describe an individual's emotions, confidence in performance, and risk appraisal related to re-engagement in sport after ACLR.

STUDY DESIGN

A single randomized control trial will compare the use of exercises augmented with BFRT with quantitative measurements of strength and patient-reported outcomes. A total of 40 youth and adolescent patients undergoing a surgical procedure for ACLR and subsequent physical therapy at our institution will be recruited for this study. Patients will be randomized into one of two groups using computer randomization for allocation:

the *intervention group* receiving BFRT as part of physical therapy, and the *control group* will follow the institution's standard ACLR rehabilitation protocol. Both groups will follow a time- and criterion-based standardized rehabilitation protocol. The primary outcomes will be isometric and isokinetic knee peak torque and limb symmetry indices. Secondary outcomes will be quadriceps hypertrophy via mid-thigh circumference and patient-reported outcomes.

Target Population

Adolescent patients between the ages of 12 and 18 will be recruited at the time of surgery, specifically, those that participate in sports who are undergoing primary ACLR reconstruction at Connecticut Children's

Study Group and Control Group Inclusion Criteria

1) Prior to surgery participated in > 50 hours/year of level I or II sports as defined by Noyes et al⁴³ and planned to return to prior level.

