Mid-thigh circumference will be used to measure and track muscle hypertrophy. Circumferential measurements has been shown to be valid and is often used after ACLR to assess quadriceps hypertrophy.⁴⁴ All subjects will be supine with the knee in full extension. The average of 3 measurements will be recorded with the starting point 10cm superior to the superior pole of the patella.

10 Repetition Max Test: The 10 repetition max test will be used to determine an estimate 1 rep maximum on the Shuttle Leg Press machine, as this is a safe and reliable alternative to predicting a 1 rep maximum. This will allow for exercise prescription.⁴⁵ All participants will complete a double leg and single leg Shuttle leg press 10 repetition maximum. The test will follow the protocol as recommended by the National Strength and Conditioning Association.⁴⁶

Isometric thigh strength: Preoperative, 8 week, 12 week, 6 month, and return to play assessments will measure maximum isometric muscle torque using an isokinetic dynamometer (Humac CSMi USA, Stoughton, MA, USA). Patients will complete 3 trials with each knee in 60° of flexion and will be allowed a 5-second rest period between trials. The uninvolved limb's quadriceps and hamstring strength will be tested first, followed by the involved limb. Patients will be given verbal encouragement throughout the test to provide maximal effort. The highest peak torque measurement of the five trials will be collected and recorded in newton-meters (Nm). These peak torque values will be used to calculate the Limb Symmetry Index (LSI), or the ratio between the involved limb and uninvolved limb and expressed as a percentage. Peak torque will subsequently be normalized to the patient's body mass (kilogram) and recorded for analysis (Nm/kg).

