Isokinetic thigh strength: For assessments at 6 months and time of return to play, maximum muscle torque will be assessed using an isokinetic dynamometer (Humac CSMi USA, Stoughton, MA, USA). Patients will be positioned in short sitting with 90 degrees of hip flexion, their trunk and thigh supported with straps, and dynamometer arm secured proximal to the ankle joint. The uninvolved limb's quadriceps and hamstring strength will be tested first, followed by the involved limb. Patients will be given verbal encouragement throughout the test to provide maximal effort. Using an isokinetic dynamometer in this manner has been shown to be a reliable method to quantify quadriceps and hamstring peak torque in adults^{47,48} and children.⁴⁹ All administrators of the isokinetic testing are trained per HUMAC NORM standardized guidelines. Isokinetic quadriceps and hamstring torque was assessed through a knee range of motion from 0 to 90°, with gravity correction applied.⁵⁰ Three practice trials will be completed, followed by ten test trails (completed at 180°/sec) and two practice trials paired with five test trials (completed at 60°/sec). The highest peak torque measurement of the five trials will be collected and recorded in newton-meters (Nm). These peak torque values will be used to calculate the Limb Symmetry Index (LSI), or, the ratio between the involved limb and uninvolved limb and expressed as a percentage. Peak torque will subsequently be normalized to the patient's body mass and recorded for analysis (Nm/kg).

Patient Reported Outcomes:

- 1) Pediatric International Knee Documentation Committee Subjective Knee Evaluation form (Pedi-IKDC)
- 2) Knee Injury and Osteoarthritis Outcome Score (KOOS)
- 3) Tegner Activity Scale
- 4) Anterior Cruciate Ligament Return to Sport Index (ACL-RSI) scale.

Data will be collected at five different time points during the rehabilitation process. Additionally, we will collect data at 2 year phone/email follow up to record patient outcomes. These assessments are completed in conjunction with the surgeon's follow up visit. The physical therapist completing the assessment will record all outcomes in a REDcap database.

Assessment time point	Data Points Collected			
Pre-op	Range of motion (Involved/Uninvolved)			
8 weeks	1) Flexion and Extension(°)			
12 weeks	HUMAC isometric knee extension at 60° (Involved/Uninvolved)			
	2) Involved/Uninvolved Peak Torque (Nm)			

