Data will be collected on all patients enrolled into the study. Descriptive statistics will be generated on the demographic characteristics of both treatment groups. We will use a two-way repeated measures analysis of variance to determine the effect of treatment groups, BFRT compared to standard of care therapy, over time on subjective and objective outcomes. Exact analysis for each test will depend on variance and distribution/normality of data set. This will be achieved using the Statistical Package for the Social Sciences (SPSS) software version 27.0 (IBM Corp., Armonk, NY, USA). We will address each aim in the following manner.

Accrual and Expected Duration of Accrual

Once approved, we expect that this study can be accomplished within two to three years. The open period for this study will be between February 2022 and February 2025.

Study Limitations:

There are several limitations anticipated with this study that will impact its power and external validity. These limitations include an inherent sampling bias with our recruitment strategy, lack of patient or participant blinding, and small sample size.

Attempts will be made to reduce any potential bias by having standardized educational scripts regarding BFR training that each treating therapist will read to subjects prior to their first BFR session.

Subjects in our study will likely come from the same surgeons and the same type of ACL graft (QT). This could be a potential limitation in the generalizability of our results to other surgeons and graft types.

Administrative Organization

Roles and responsibilities:

[name], PT, DPT: Will serve as the study's primary investigator. [name] will provide primary support for the SRC and IRB study protocol development and submission, as well as maintaining updates and compliance with clinicaltrials.gov. He will review the required databases and pull the relevant data required to complete this study. He will also aid in data interpretation and manuscript preparation.

All MDs listed: The MDs listed on this proposal will be responsible for recruitment of patients, data interpretation and manuscript preparation.

All physical therapists listed: The PT's listed on this proposal will serve as the study's co-investigator. They will provide support in development of SRC and IRB documents (review of literature). They will help with data collection, recruitment, consenting patients.

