[name]: [name] is ATC in Sports Medicine who will assist with relcruitment, consenting, and data collection. She also will serve as the study coordinator.

[name], [name]: Our exercise technologists listed will assist with consenting, as well as data collection during testing times, and organizing tabulated results.

[name], ATC, PhD: [name] is a researcher at UCONN Sports Medicine Institute. She will be assisting in study design, data interpretation and preparation, statistical analysis and manuscript preparation:

Data Collection and Management

a. Data collection forms: All data points and outcome measures will be completed and entered into a REDcap database to facilitate data analysis.

b. Data collection software: The Research Operations and Development team assisted with the development of this REDCap project. Connecticut Children's has licensed this software toolset and workflow methodology for electronic collection and management of research data. REDCap (Research Electronic Data Capture) data collection projects rely on a thorough study. The development and testing process results in a well–planned data collection strategy for studies. This project will use REDCap data transactions due to the web–based information transmission being encrypted. REDCap was developed specifically around HIPAA–Security guidelines. REDCap has been disseminated for use locally at other institutions and currently supports over 5854 academic/non-profit consortium partners and over 2.1 million research end–users (www.project-redcap.org)[name] will oversee data management. The data will be collected by investigators, and it will be entered into REDCap by [name] and [name] to insure data accuracy. Statistics will be run using Microsoft Excel and SPSS.

d. [name] will oversee data management. The data will be collected by investigators, and it will be stored only in REDcap. The database will only be accessible to those individuals included in this study.

e. Information will be reviewed prior to de-identification to insure there are no errors with transcription.

f. Data quality assurance: Data that is collected will be manually verified to ensure that no information has been entered into REDcap incorrectly. Additionally, we will randomly check 10% of data in the REDcap database for accuracy after initial entry to insure accuracy

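### Effort-dependent primary strength tests use verbal encouragement with no fixed wording, and the protocol neither masks the tester nor separates testing from treatment

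*Protocol*

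**What the plan says.** Protocol, *Study Design*: "The primary outcomes will be isometric and isokinetic knee peak torque and limb symmetry indices".

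Protocol, *Isometric thigh strength* and *Isokinetic thigh strength*: both tests seek a maximal voluntary contraction. The uninvolved limb is tested first and the involved limb second, and the highest peak torque is kept. Both paragraphs contain the sentence "Patients will be given verbal encouragement throughout the test to provide maximal effort". Neither gives a script or a limit. The only statement on testers is in the isokinetic paragraph: "All administrators of the isokinetic testing are trained per HUMAC NORM standardized guidelines".

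Protocol, *Patient Reported Outcomes* (the paragraph before the table of data points): assessments coincide with the surgeon's follow-up visit, and "The physical therapist completing the assessment will record all outcomes in a REDcap database".

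Protocol, *Roles and responsibilities*: the listed physical therapists are co-investigators, and "They will help with data collection, recruitment, consenting patients". The exercise technologists assist with consenting, "as well as data collection during testing times", and with organizing results.

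Protocol, *Study Limitations*: the blinding limitation reads "lack of patient or participant blinding, and small sample size". The one bias measure offered is an educational script that the treating therapist reads before the first BFR session.

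**The concern.** A dynamometer reads torque objectively, but the effort behind the reading is voluntary and responds to the person urging the patient on. If that person knows the arm and expects one arm to do better, encouragement can differ between arms without anyone intending it. The difference then enters the primary outcome directly.

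Three safeguards are usual: a tester who does not know the arm, a tester who does not treat the patient, and fixed wording for encouragement. The protocol states none of them and does not list unmasked assessment as a limitation. These are matters of trial conduct that belong in a protocol, so an analysis plan that is not at hand would not normally supply them. At stake is whether a difference in torque between the arms can be attributed to BFRT.

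**Working it through.** The protocol gives no figure on this point, so the main check is a reading of every place that deals with testing, staff or blinding. A calculation then shows how sensitive the trial would be.

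**1. Safeguards sought**

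| Safeguard | What the protocol contains |
|---|---|
| Tester masked to arm | Nothing in the testing paragraphs, *Roles and responsibilities*, or *Data Collection and Management* |
| Tester is not the treating therapist | Not stated. Physical therapists deliver treatment, and a physical therapist completes the assessment |
| Fixed encouragement wording | Not stated for either test |
| Standardised technique | Training on the device, stated for isokinetic testing only. It masks no one |
| Bias named as a limitation | Patients or participants only, not assessors |
| Bias measure | Script before the first BFR session, which does not concern testing |

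**2. Which primary outcomes are exposed**

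Let *I* and *U* be the peak torques of the involved and uninvolved limbs, so LSI = 100 × *I*/*U*. Suppose encouragement multiplies effort by (1 + *e*).

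- Peak torque of the involved limb becomes *I*(1 + *e*), so it is fully exposed.
- If both limbs are raised equally, LSI = 100 × *I*(1 + *e*)/[*U*(1 + *e*)], which is unchanged.
- If only the involved limb is raised, LSI is multiplied by (1 + *e*).

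LSI is therefore protected only if encouragement is the same for both limbs, and the protocol does not require that.

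**3. Illustration of size**

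Inputs: *n* = 20 per arm and alpha 0.05, both from *Sample Size/Power Analysis*. The two-sided test, a true effect of zero and the shift *b* in SD units are assumptions. The protocol gives neither an SD nor any estimate of tester influence.

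Method: a two-sample t-test at one time point, with df = 2 × 20 − 2 = 38 and critical value 2.024. The non-centrality is *b* × √(*n*/2) = *b* × √10 = 3.162*b*. The false-positive rate is the probability that a non-central t with 38 df falls beyond ±2.024.

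| Assumed shift *b* (SD) | Non-centrality | False-positive rate |
|---|---|---|
| 0 | 0 | 5.0% |
| 0.1 | 0.316 | 6.1% |
| 0.2 | 0.632 | 9.5% |
| 0.3 | 0.949 | 15.2% |

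This is one simple comparison and not the planned two-way repeated measures analysis of variance. It shows an order of magnitude and does not predict the trial's error rate.

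**The case against.** **The protocol does not say that the tester knows the arm or treats the patient.** This stands. A reader might infer from the sentence on recording outcomes that the treating therapist tests unmasked. That sentence says only that a physical therapist completes the assessment and records it. Visits tied to the surgeon's follow-up might even be staffed separately from treatment. *Data Collection and Management* also has investigators collect the data and two named staff enter them. The point is therefore limited to masking and separation not being stated.

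**Existing staff may not be able to test masked.** This stands in part. A reader might infer that the exercise technologists could simply take over. The protocol says that they assist, which does not show that they may run maximal tests alone. They also help organize results, and database access is open to those on the study. *Budget Justification* bills assessments through sports physical therapists, and its assessment code covers 12 weeks, 6 months and return to play but does not list 8 weeks. A non-treating therapist is the simpler option, since several are listed.

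**The size is overstated.** The shift is assumed, and 0.1 SD moves 5% only to 6.1%. Equal encouragement of both limbs would cancel in the LSI. A reader might infer larger inflation from a baseline-adjusted analysis. That would need an analysis and a correlation the protocol does not give, and isokinetic strength has no pre-operative measurement in Table 1. A reader might also infer that testers can choose which trials count. The text takes the highest value, so this is not an open judgement. The isometric paragraph does specify three trials and then takes the best of five, which is a separate inconsistency.

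**Patients are unmasked anyway.** This is true and disclosed. They control their own effort, so masking the tester removes only part of the bias. The tester's part is nevertheless the part that the study team can control.

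**Conclusion.** The point holds in this limited form. The primary strength outcomes depend on effort, encouragement has no fixed wording, and the protocol neither masks the tester nor states that the tester is not the treating therapist. Its limitations do not mention assessors. Followed as written, the plan allows tester-driven bias in peak torque, and in LSI if encouragement differs between limbs. It does not show that such bias will occur.

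The size cannot be derived from the protocol. On the assumptions of 20 per arm, no true effect and a single two-sided comparison, shifts of 0.1 to 0.3 SD would give false-positive rates of 6.1% to 15.2% instead of 5%. The change is worth making because it is cheap and can largely draw on staff already listed.

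**What to change.** In the protocol's testing sections:

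- State that strength testing at 8 weeks, 12 weeks, 6 months and return to play is done by a listed physical therapist who does not treat that patient and is not told the arm. An exercise technologist may do it instead if qualified and if this is compatible with the billing arrangement in *Budget Justification*.
- Fix one encouragement script, the same for both limbs and both arms.
- Ask patients before each test not to disclose their group.
- Keep allocation off the testing form and hidden from testers in REDCap.
- Have the tester record whether the arm became known.
- Say consistently who records and who enters the outcomes, since the *Patient Reported Outcomes* paragraph and *Data Collection and Management* differ.
- Add unmasked assessment to *Study Limitations* wherever masking is not achieved.

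**Cost:** rota planning, a short script, a change to REDCap access and a check of the billing. Masking will be imperfect because patients may reveal their group. Patients remain unmasked, so the change reduces only the tester's share of the bias. The sample size is unaffected.

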	3) Involved/Uninvolved Peak Torque normalized to bodyweight (Peak torque/bodyweight) (Nm-Kg)			
	4) Quadriceps Limb Symmetry Index (LSI)=Knee extension peak torque involved/knee extension peak torque uninvolved*100			

	HUMAC isometric knee flexion at 60° (Involved/Uninvolved)
	5) Involved/Uninvolved Peak Torque (Nm)
	6) Hamstring deficit=Knee extension peak torque involved/knee extension peak torque uninvolved*100
	7) Involved/Uninvolved Peak Torque normalized to bodyweight (Peak torque/bodyweight) (Nm-Kg)
	Quadriceps hypertrophy thigh circumference (Involved/Uninvolved)
	8) Measured at 10cm above the superior pole of the patella bilaterally
	Patient Reported Outcome Measures
	9) Pedi-IKDC
	10) ACL-RSI
	11) KOOS
6 months	Range of motion (Involved/Uninvolved)
9 months	1) Flexion and Extension(°)
	HUMAC isometric knee extension at 60° (Involved/Uninvolved)
	2) Involved/Uninvolved Peak Torque (Nm)
	3) Involved/Uninvolved Peak Torque normalized to bodyweight (Peak torque/bodyweight) (Nm-Kg)
	4) Quadriceps LSI= Knee extension peak torque involved/knee extension peak torque uninvolved*100
	HUMAC isometric knee flexion at 60° (Involved/Uninvolved)
	5) Involved/Uninvolved Peak Torque (Nm)
	6) Hamstring deficit=Knee extension peak torque involved/knee extension peak torque uninvolved*100
	7) Involved/Uninvolved Peak Torque normalized to bodyweight (Peak torque/bodyweight) (Nm-Kg)
	Isokinetic knee extension at 180%sec, and 60%sec
	8) Involved/Uninvolved Peak Torque (Nm)
	9) Quadriceps deficit=Knee extension peak torque involved/knee extension peak torque uninvolved*100
	10) Involved/Uninvolved Peak Torque normalized to bodyweight (Peak torque/bodyweight) (Nm-Kg)
	Isokinetic knee flexion at 180%sec, and 60%sec
	11) Involved/Uninvolved Peak Torque (Nm)
	12) Hamstring deficit=Knee extension peak torque involved/knee extension peak torque uninvolved*100
	13) Involved/Uninvolved Peak Torque normalized to bodyweight (Peak torque/bodyweight) (Nm-Kg)
	Quadriceps hypertrophy thigh circumference (Involved/Uninvolved)

	14) Measured at 10cm above the superior pole of the patella bilaterally
	Patient Reported Outcome Measures
	15) Pedi-IKDC
	16) ACL-RSI
	17) KOOS
2 years	Patient Reported Outcome Measures
	1) Pedi-IKDC
	2) ACL-RSI
	3) KOOS

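### The hamstring index is defined with knee-extension torque in three table entries, and the isometric peak is taken from five trials in a test of three

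*Protocol*

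**What the plan says.** **Hamstring index.** The table of data points by assessment time has one block for the pre-operative, 8-week and 12-week visits and one for 6 and 9 months. Both blocks contain a group headed "HUMAC isometric knee flexion at 60" degrees. The later block adds a group headed "Isokinetic knee flexion at" two speeds. Each of these three groups has an entry that reads "Hamstring deficit=Knee extension peak torque involved/knee extension peak torque uninvolved*100": item 6 in the early block, and items 6 and 12 in the later block. For the quadriceps, item 4 of the early block reads "Quadriceps Limb Symmetry Index (LSI)=Knee extension peak torque involved/knee extension peak torque uninvolved*100".

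The text on isometric and isokinetic thigh strength says of the uninvolved limb that its "quadriceps and hamstring strength will be tested first, followed by the involved limb". It describes the index as "the ratio between the involved limb and uninvolved limb and expressed as a percentage", calculated from the peak torques recorded.

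**Isometric trial count.** Under Isometric thigh strength in the Data Collection section, the Protocol says "Patients will complete 3 trials with each knee". A few lines later it says "The highest peak torque measurement of the five trials will be collected and recorded in newton-meters". The second sentence also appears under Isokinetic thigh strength, where five test trials are done at 60 degrees per second and ten at 180.

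**The concern.** A hamstring symmetry index has to use knee-flexion torque. The three entries use extension torque, so the formula contradicts its own label, its heading and the text that describes the test. The Appendices section says the REDCap database will be built to include the data points listed. A calculated field copied from the table would therefore store the quadriceps ratio under a hamstring name.

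The trial count matters more, because it concerns how a primary outcome is recorded. The Study Design section names isometric peak torque and limb symmetry among the primary outcomes. Hypothesis 1a compares them at 8 and 12 weeks. Hypothesis 1c concerns change in strength from before surgery to 8 weeks, and Table 1 schedules only isometric testing at those two visits. A maximum tends to rise with the number of attempts, so the count is part of the definition of the endpoint.

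**Working it through.** The Protocol states no figure to reproduce here. The check is a comparison of the text, with counts to show the reach and one illustrative calculation.

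**1. Hamstring formula against quadriceps formula**

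| Block | Hamstring entry (flexion heading) | Torque used | Quadriceps entry | Torque used |
|---|---|---|---|---|
| Pre-op, 8, 12 weeks, isometric | item 6 | extension | item 4 | extension |
| 6, 9 months, isometric | item 6 | extension | item 4 | extension |
| 6, 9 months, isokinetic | item 12 | extension | item 9 | extension |

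In every row both sides equal 100 × (extension torque, involved) / (extension torque, uninvolved). All three hamstring entries are therefore algebraically the same as the quadriceps entries. The flexion torques needed for the correct ratio are collected in item 5 of each block and in item 11 of the later block.

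Reach, if the formula is followed literally and every visit is completed:
- Isometric: 5 visits × 1 index = 5.
- Isokinetic: 2 visits × 2 speeds = 4.
- Per patient: 5 + 4 = 9. For 40 patients: 9 × 40 = 360.

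**2. Isometric trial count**

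Three trials per knee means three for one limb or six for both. Neither is five. No other section gives an isometric count. The repeated sentence has something to refer to in the isokinetic section, but only in the test at 60 degrees per second.

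Reach, again with all visits completed:
- All isometric peaks: 5 visits × 2 limbs × 2 muscle groups = 20 per patient; 20 × 40 = 800.
- Extension peaks behind Hypotheses 1a and 1c: 3 visits (pre-op, 8 and 12 weeks) × 2 limbs = 6 per patient; 6 × 40 = 240.

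**3. How much the count could matter (illustration)**

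For n independent standard normal trials, the expected maximum is E(n) = ∫ x · n · φ(x) · Φ(x)^(n−1) dx. Numerical integration gives:
- E(3) = 0.8463
- E(5) = 1.1630
- Difference = 1.1630 − 0.8463 = 0.3167, or about 0.32 within-session SD

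The Protocol gives no within-session SD, so this cannot be converted to Nm, Nm/kg or points of limb symmetry.

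**The case against.** The case on the other side is that both points are copying slips with little consequence.

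- **Hamstring entries.** The label, the heading and the neighbouring flexion-torque items all point to one sensible reading, and the text describes the index correctly. No hypothesis names it. This stands, and it keeps the point small. It does not make the formula right, because the table is the only place that writes out the formula for each muscle group. The data collection form mentioned in the Appendices section is not available, so it is not known whether the wrong formula reached a database field.
- **Trial count.** The instruction to the tester is three trials, and the reference to five looks carried over from the isokinetic text. On either reading the highest trial performed is recorded, and nothing suggests the count would differ by arm, limb or visit. This is the strongest objection, and it limits the effect. Even so, the Protocol does not say which number is intended, and the isokinetic sentence is itself a loose reference because it fits only one of the two speeds.
- **Size.** The totals of 360, 800 and 240 count data fields and do not measure an effect. The 0.32 SD needs counts that vary between sessions, and independent trials. With rests of 5 seconds between maximal efforts, fatigue or learning makes independence doubtful. This is accepted: the figure is an illustration only.

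**Conclusion.** Both inconsistencies are real, and both are minor. All three hamstring entries give the quadriceps ratio. Taken literally they would make 9 values per patient wrong (360 for 40 patients with complete visits), all recoverable from the flexion torques collected and none used in a stated hypothesis. The isometric recording rule asks for the highest of five trials when three are performed, so it cannot be followed as written, and it defines a primary outcome.

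With one uniform count there is no shift between visits. Both arms have the same test, so no bias between arms is shown. Only a count that varied between sessions would move the expected peak, by about 0.32 within-session SD under independent normal trials. Neither point casts doubt on the primary comparison itself.

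**What to change.** - **Hamstring entries (item 6 in both blocks, item 12 in the later block).** Define the index as 100 × (knee-flexion peak torque of the involved limb) / (knee-flexion peak torque of the uninvolved limb). Labelling it a limb symmetry index, as the strength-testing text does, would be clearer but is optional. If a database field already uses the extension formula, recompute it from the stored flexion torques.
- **Isometric thigh strength.** Reconcile the two sentences to a single trial count, the same for both limbs, all visits and both arms, and record the highest of that number. The Protocol does not show which count is intended, so the investigators must settle it.

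The cost is one word in three table lines and one number in the isometric section. No new measurement is needed, and the sample size does not change.
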